11.4. Safety Analyses

The key safety endpoints will include:

- Percentage of subjects with kidney stones
- Change from baseline in weight Z-score over time
- The following height analyses will be conducted for prepubertal subjects (2 to 9 years of age), subjects 10 to 15 years of age, and subjects 2 to 15 years of age:
 - Height at 1 year postbaseline
 - Height change from baseline over time
 - Height Z-score at 1 year postbaseline
 - Change from baseline in height Z-score over time
 - Height velocity at 1 year postbaseline
 - Height velocity Z-score at 1 year postbaseline
 - Percentage of outlier subjects with height Z-score decrease of >0.5 , >1.0 , and >2.0 over time
- The following BMD and BMC endpoints:

- BMD and BMC over time
 - BMD and BMC change from baseline over time
 - Z-score for BMD and BMC over time
 - Change from baseline in Z-score for BMD and BMC over time
 - Percent change from baseline in BMD and BMC over time
 - Percentage of outlier subjects with BMD Z-score decrease of >0.5 , >1.0 , and >2.0 over time
- Change from baseline in biochemical markers of bone mineralization including: serum levels of alkaline phosphatase, calcium, phosphorus, parathyroid hormone (intact), 25-hydroxy-vitamin D, 1,25-dihydroxy vitamin D, and IGF-1
 - Change from baseline in serum and urine laboratory tests, eg, bicarbonate, ammonia, renal function tests, and LFTs
 - Change from baseline in bone age

Z-scores for the DEXA scans will be calculated locally at baseline and at M12 to determine eligibility for the study and the Post-Study Follow-Up phase, and centrally for all statistical analyses. The Z-score calculation will take the DEXA machine and the subject's age, sex, height, and ethnicity into consideration. The reference databases for calculating the Z-scores are provided in the DEXA Manual for this study.

Longitudinal endpoints will be analyzed using a mixed-model repeated measures (MMRM) analysis. The MMRM model will include treatment group, age group, visit, treatment-by-visit interaction, baseline measure, and baseline-by-visit interaction. An unstructured covariance will be used. Other appropriate covariance structures will be explored as needed. Confidence intervals with 95% confidence for the estimated treatment differences will be provided at each time point as appropriate. For proportion endpoints, 95% confidence intervals will be provided for the treatment difference. Each of the endpoints will also be summarized by age group.

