7. SAFETY

The safety variables to be summarized include kidney stones, height, weight, BMD and bone mineral content (BMC), biochemical markers of bone mineralization, bone age XR, seizure counts, cognitive, developmental, and behavioral assessments, treatment-emergent AEs, Columbia-Suicide Severity Rating Scale (C-SSRS), cognitive, developmental and behavioral assessments (COGSTATE computerized battery and NEPSY Language scale; Vineland Adaptive Behavioral Scale, Child Behavior Checklist (CBCL)), clinical laboratory tests (hematology, chemistry, urinalysis, and 24-hour urine collection), vital signs and physical exam. Safety variables are to be tabulated by descriptive statistics (n, mean, median, SD, minimum, and maximum; or n and percent). No formal statistical testing is planned.

For markedly abnormal labs and vital signs, age will be calculated at each visit to determine the criteria. Similarly, Vineland, CBCL and Cogstate will be calculated by age at each visit.

Z-scores for weight and height will be calculated using the SAS programs provided by the Centers for Disease Control (CDC) for the calculation of the 2000 CDC growth charts. Z-scores for the BMD and BMC will be provided by the central DEXA reading center (Bioclinica).

Z-scores for the DEXA scans will be calculated locally at baseline only to determine eligibility for the study, and centrally for all statistical analyses. The Z-score calculation will take the DEXA machine and the subject's age, sex, height, and ethnicity into consideration. The reference databases for calculating the Z-scores are provided in the DEXA Manual for this study (please see the imaging charter of attachment 1 for more details).

Longitudinal endpoints will be analyzed using a mixed-model repeated measures (MMRM) analysis. An MMRM analysis is included as sensitivity analysis to explore longitudinal safety data and will be analyzed in the following order.

1. The model includes treatment group, study center, age group (4 age groups), visit, treatment-by-visit interaction, baseline measure, and baseline-by-visit interaction with the unstructured covariance matrix.
2. If this model experiences convergence issues, then the same model with compound symmetric matrix followed by AR1 will be explored instead of unstructured.

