3. If the above doesn't work, then a reduced model with treatment group, age group, visit, treatment-by-visit interaction, and baseline measure will be explored. Age will be collapsed to two categories: 2-9 years of age (pre-pubertal) and 10-15 years of age (pubertal). The unstructured covariance matrix will be explored first and if it doesn't work, then compound symmetric followed by AR1 will be applied.
4. If above doesn't work, then no additional MMRM analysis will be performed. 95% CI for the estimated treatment differences will be provided.

Example of MMRM is as follows:

```
ods output estimates=est;
PROC MIXED data=dat method=REML noclprint=10;
CLASS trt center usubjid age_group visit;
MODEL change=trt base visit center age_group trt*visit base*visit /
solution; repeated visit / type=un subject=usubjid;
lsmeans trt/diff cl;
```

Sensitivity analyses for height z-scores, weight-z-scores and BMD z-scores will be conducted for subset of safety analysis set: for subjects who started taking at least one concomitant AED, data collected after the start of taking AED medication will be excluded from the analysis.

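### If the unstructured MMRM fails, the SAP falls back to constant-variance structures, so the Month 12 interval is too narrow if the spread of change grows over visits

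*SAP*

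**What the plan says.** SAP section 7 sets out a four-step ladder for the longitudinal endpoints.

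- Step 1 has treatment, center, four age groups, visit, treatment-by-visit, "baseline measure, and baseline-by-visit interaction with the unstructured covariance matrix".
- Step 2: "If this model experiences convergence issues, then the same model with compound symmetric matrix followed by AR1 will be explored instead of unstructured".
- Step 3 drops center and baseline-by-visit, collapses age to two groups, and starts again: "The unstructured covariance matrix will be explored first and if it doesn't work, then compound symmetric followed by AR1 will be applied".
- Step 4: "If above doesn't work, then no additional MMRM analysis will be performed". The same item then adds: "95% CI for the estimated treatment differences will be provided".

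The example code has "PROC MIXED data=dat method=REML noclprint=10" and "repeated visit / type=un subject=usubjid". It has no EMPIRICAL option, and its LS-means line asks for the treatment difference averaged over visits. Protocol 11.4 is more specific about timing: "Confidence intervals with 95% confidence for the estimated treatment differences will be provided at each time point as appropriate".

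The same SAP section labels the MMRM a sensitivity analysis, tabulates the safety variables descriptively and plans no formal tests. SAP section 1 lists the key endpoints as the Month 12 changes in BMD, height and weight Z-score.

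**The concern.** The outcome is change from baseline. One month after baseline, children have had little time to diverge; by Month 12 they have had a year. CS and AR1 in their plain forms estimate a single variance for all visits, so the Month 12 standard error is built from an average that includes the small early variances. No heterogeneous form is named, and nothing in the code corrects the errors afterwards.

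The order of the steps makes this worse. The first response to a convergence problem is to change the covariance, not to remove center or baseline-by-visit. Because CS rarely fails, the ladder would normally stop there.

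At stake is the error bar on the Month 12 difference, for which SAP 2.4 sets its precision targets. Sections 7.2 to 7.4 give no other between-arm estimate with an interval for weight, height or BMD.

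**Working it through.** **Planned precision (SAP 2.4).** Half-width = 1.96 × SD × √(2/n).

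- Height: 1.96 × 0.28 × √(2/53) = 0.107 (plan: 0.11).
- Weight: 1.96 × 0.43 × √(2/100) = 0.119 (plan: 0.12).
- BMD: 1.96 × 0.40 × √(2/100) = 0.111 (plan: 0.12, which needs rounding up).

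**Number of parameters.** Height and weight have five post-baseline visits (Months 1, 3, 6, 9, 12; SAP Table 2), so UN has 5 × 6/2 = 15 covariance parameters. DEXA has two (Months 6, 12; SAP Table 8), so UN has 2 × 3/2 = 3. CS has 2 in either case.

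**What CS does to Month 12.** With complete data and free treatment-by-visit means, the CS variance is the mean of the visit variances. Define

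R = √(mean of visit variances / Month 12 variance).

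The printed Month 12 interval is R times the correct width, and its true coverage is 2Φ(1.96R) − 1.

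**Assumed variance path.** The documents do not give one. Take Month 12 variance = a growth part plus constant noise with share f, where f runs from 0.05 to 0.75.

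- Random slope (variance ∝ t²): mean growth factor = (1 + 9 + 36 + 81 + 144)/(5 × 144) = 0.376, so R = √(0.376(1 − f) + f).
- Random walk (variance ∝ t): mean growth factor = (1 + 3 + 6 + 9 + 12)/(5 × 12) = 0.517, so R = √(0.517(1 − f) + f).

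| f | Slope: R, coverage | Walk: R, coverage |
|---|---|---|
| 0.05 | 0.64, 79% | 0.74, 85% |
| 0.25 | 0.73, 85% | 0.80, 88% |
| 0.50 | 0.83, 90% | 0.87, 91% |
| 0.75 | 0.92, 93% | 0.94, 93% |

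AR1 fits give similar values (for example 0.68 and 82% at slope, f = 0.05). With the planned 29% dropout spread over visits, the lowest values are 0.59 for CS (75%) and 0.63 for AR1 (78%). The overall range for R is 0.59 to 0.94, so the interval is 6% to 41% too narrow. At f = 0.25 it is 0.70 to 0.80, coverage 83% to 88%.

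In the plan's units, with complete data, the height half-width of 0.107 would print as 0.64 × 0.107 = 0.068 up to 0.94 × 0.107 = 0.100. The weight half-width of 0.119 would print as 0.076 to 0.112.

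**A check tied to the SAP's own tables.** For height change in cm, Appendix 6 lists normative velocity SDs of about 0.5 to 1.4 cm/year. Take 1.0 cm/year accumulating linearly, with an assumed noise SD in change of 0.3 to 0.7 cm.

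- Noise 0.3: R = √((0.376 + 0.09)/(1 + 0.09)) = 0.65, coverage 80%.
- Noise 0.7: R = √((0.376 + 0.49)/(1 + 0.49)) = 0.76, coverage 86%.

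**BMD.** The growth factor is (36 + 144)/(2 × 144) = 0.625 for a slope and (6 + 12)/(2 × 12) = 0.75 for a walk. R runs from 0.80 (slope, f = 0.05) to 0.97 (walk, f = 0.75), and down to 0.77 with dropout. Coverage is 87% to 94%.

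**The contrast in the example code.** For the equal-weight average over visits, CS preserves the sum of all covariance entries when data are complete, so R = 1.00 and coverage is 95%. With 29% dropout, R is 0.87 to 0.99 and coverage 91% to 95%. AR1 gives 0.89 to 1.16, coverage 92% to 98%.

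**The case against.** The strongest reply is that little depends on this. The MMRM is exploratory, no test is planned, and the coded contrast is the visit average, for which CS is close to valid. That stands, and it limits the point to by-visit estimates. It does not remove it, because protocol 11.4 calls for intervals at each time point and the SAP's key endpoints are at Month 12.

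A reader might infer that the Month 12 intervals would be far too narrow. The documents do not support that as a general statement. They give SDs at 1 year only, and the severe figures need a fast-spreading path with little measurement noise; slower paths cost 1 or 2 points of coverage.

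A reader might also infer that early termination makes the fallback likely. SAP section 1 does not say how many children had been enrolled, and no UN failure rate is available. For DEXA, with three parameters, failure is unlikely.

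Finally, step 4 might be read as leaving no treatment difference at all. To reach it, CS would have to fail in two mean models, which is close to impossible. Descriptive summaries would remain, and the item still promises a 95% interval. The gap is only that no estimator is named for it.

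Part of the remedy is also already in the plan: step 3 does drop center and return to UN. The fault is its place in the sequence.

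**Conclusion.** The point holds in a conditional form. If UN does not converge, and if the variance of change grows over visits, the rule as written gives Month 12 intervals that are too narrow for height and weight, with coverage of about 75% to 93% against a nominal 95%. For BMD the loss is modest and the trigger improbable. The direction is the same on every growing-variance path examined; the size rests on the assumed path, the noise share and, for the lowest values, 29% dropout spread over visits. The visit-averaged difference under CS is little affected. This is worth correcting because the rule is explicit and the repair is cheap, but it does not threaten the main, descriptive analysis.

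**What to change.** In SAP section 7:

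1. On UN failure, simplify the mean model first and keep UN: drop center, then baseline-by-visit. In effect, move the reduced UN model of step 3 ahead of step 2.
2. Only if that fails, use a heterogeneous-variance structure (TOEPH, ARH(1) or CSH) in place of CS and AR1. Report sandwich errors as a check, noting that they can be too small in small samples.
3. Request treatment-by-visit LS means so that the Month 12 difference and its interval are reported.
4. Name the estimator for the 95% interval if no MMRM converges, for example an ANCOVA of Month 12 change on treatment, baseline and age group. State that it uses only children with Month 12 data.

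Kenward-Roger degrees of freedom with UN are optional. The cost is a few lines of text and code, and somewhat wider intervals when a fallback is used.

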1. CHANGES IN CONDUCT OF THE STUDY

On 12 December 2018, the independent Data Monitoring Committee (DMC) recommended to stop the TOPMATEPY4067 study because of futility of study enrollment. On 12 August 2019, Janssen has received the US FDA decision as follows:

- Stop enrolling new subjects at all sites and discontinue the study at all the sites that do not have either subject under study treatment or subjects who require a repeat bone mineral density (BMD) measurement 6 months after discontinuing study treatment.
- All sites with any subject on treatment in the study should continue following the subject according to the protocol until treatment has been completed, the subject has discontinued prematurely, or a repeat DEXA scan (which is indicated 6 months after treatment discontinuation) has been completed.

The US FDA decision is based on the slow rate of study enrollment of subjects despite continuous efforts to improve recruitment in the study. The decision is not related to any safety issues.

Interim analyses on the key endpoints (change in BMD z-score at Month 12, change in height z-score at Month 12 and change in weight z-score at Month 12) were conducted on 13 December 2018. This SAP has been modified based on the early termination of the study.

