2.4. Sample Size Justification

A total of 282 randomized subjects, 141 in each treatment group, will be enrolled in the study. The sample size takes into account a 1-year dropout rate of 29%, which is a conservative estimate based on the dropout rates was observed in a previous monotherapy study in the 6- to 15-year-old age group, Study TOPMAT-EPMN-106, including a dropout rate of 22% in the study overall (both double-blind and open-label phases) and a dropout rate of 35% for the double-blind phase. The sample size was estimated in order to achieve a sufficient precision for the estimates of the treatment effect on the key endpoints. The precision of the confidence interval (CI) estimates for the key safety parameters are shown below:

- Annual change in BMD (L1-L4) Z-score: In the Bone Mineral Density in Childhood Study (BMDCS), mean annual change in BMD (L1-L4) Z-score in 6- to 15-year-old healthy subjects was, as expected, minimal (0.01-0.07). The standard deviation (SD) varied from 0.3 to 0.48 across sex and age groups. Assuming an SD of 0.4, with 100 completed subjects per group, the 95% CI for the treatment difference will have a precision of 0.12.

- Annual change in height Z-score in the 2- to 9-year-old age group: In the monotherapy epilepsy study TOPMAT-EPMN-106, the observed change from baseline in mean height Z-score at 1 year among the 2- to 9-year-old subjects treated with topiramate 400 mg/day was -0.18, with an SD of 0.28. Assuming that 53% of the subjects will be recruited in the 2 to 9-year-old age group, i.e., 53 completed subjects per treatment group, the 95% CI for the treatment difference will have a precision of 0.11.
- Change in weight Z-score in the 2- to 15-year-old age group: In the monotherapy epilepsy study TOPMAT-EPMN-106, a -0.59 decrease from baseline in weight Z-score, with an SD of 0.43, was observed after 1 year of treatment with topiramate 400 mg/day. Assuming an SD of 0.43, a sample size of 100 completed subjects per treatment group will provide a 95% CI with a precision of 0.12.

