2.6. Time and Events Schedule

The flow chart showing trial phases and timing of treatment and assessments is given in [Table 1](#).

Table 1: Time and Events Schedule

Phase	Screening	Open-Label Treatment ^a						End-of-Study/Early Withdrawal	Follow-up Telephone Contact
		Baseline/ W1	M1	M2	M3	M6	M9		
Week(W)/Month(M)									
Study Day	≤-28	1 ^c	30	60	90	180	270	360	390 ^d
Study Day Window	-7days	±7days	±7days	±7days	±7days	±7days	±7days	±7days	±7days
Visit ^e	1	2	3	4	5	6	7	8	NA
Screening/Administrative									
Informed consent and assent	X								
Inclusion/exclusion criteria	X	X							
Medical/seizure history	X	X							
Physical activity evaluation ^f	X								
Prestudy AED and other therapy ^g	X								
Randomization		X							
Study Drug									
Dispense study drug		X	X	X	X	X	X		
Study drug accountability			X	X	X	X	X	X	
Pharmacokinetics									
Blood sample collection for quantitation of study drug ^h			X		X	X		X	
Safety									
Physical examination	X	X	X		X	X	X	X	
Neurologic examination	X	X	X		X	X	X	X	
12-lead ECG	X								
Height/weight ⁱ	X	X	X		X	X	X	X	
Vital signs (temperature, HR, RR, BP) ^j	X	X	X		X	X	X	X	
Clinical laboratory tests ^k	X		X		X	X	X	X	
Pregnancy test ^l	X	X	X	X	X	X	X	X	
24-hour urine collection ^m	X					X		X	
Tanner staging ⁿ		X				X		X	

CONFIDENTIAL – FOIA Exemptions Apply in U.S.

Table 1: Time and Events Schedule

Phase	Screening	Open-Label Treatment ^a						End-of-Study/Early Withdrawal	Follow-up Telephone Contact
		Baseline/ W1	M1	M2	M3	M6	M9		
Week(W)/Month(M)									
Study Day	≤-28	1 ^c	30	60	90	180	270	360	390 ^d
Study Day Window	-7days	±7days	±7days	±7days	±7days	±7days	±7days	±7days	±7days
Visit ^e	1	2	3	4	5	6	7	8	NA
Renal ultrasound	X					X		X	
Biochemical bone markers	X					X		X	
DEXA scan ^{b,q}		X				X		X	
Bone age x-ray		X						X	
Dispense seizure diary and take-		X	X	X	X	X	X		
Review seizure diary and take-			X	X	X	X	X	X	
Cogstate Battery ^r	X	X				X		X	
Animal Fluency Test NEPSY-II ^u	X	X				X		X	
Vineland Adaptive Behavior Scale ^v		X			X	X		X	
CBCL-Parent Version ^w		X			X	X		X	
C-SSRS ^x		X	X	X	X	X	X	X	
Ongoing Review									
Concomitant therapy	X	X	X	X	X	X	X	X	X
Adverse event monitoring	X	X	X	X	X	X	X	X	X

Footnotes appear on the following page.

^a Includes a titration period of approximately 6 to 8 weeks, followed by a maintenance period.

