7.3. Height

Observed height values, change from baseline, Z-scores for height, change from baseline in Z-scores for height, height velocity at 1 year, and height velocity Z-score will be summarized by visit using descriptive statistics. Height, Z-scores for height, height velocity and height velocity Z-scores will be calculated as the mean of the three measurements. The number and percentage of subjects with a height Z-score decrease of >0.5 , >1.0 , and >2.0 will be listed and summarized by visit using descriptive statistics. MMRM analysis will also be performed for changes from baseline and changes in Z-Scores from baseline.

The change in height z-scores will also be summarized by subject's serum bicarbonate categories.

Height velocity values and associated Z-scores will be computed for each post-baseline year in the study, based on the methods described in [Appendix 6](#).

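### The SAP's MMRM code gives a treatment difference averaged over all visits, not the Month 12 difference the study was planned around

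*SAP*

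**What the plan says.** SAP Section 7 gives example PROC MIXED code with the model line "MODEL change=trt base visit center age_group trt*visit base*visit", an unstructured covariance over visits, and one LS-means request, "lsmeans trt/diff cl". The accompanying text says "95% CI for the estimated treatment differences will be provided" and names no visit. Protocol Section 11.4 is more specific: "Confidence intervals with 95% confidence for the estimated treatment differences will be provided at each time point as appropriate".

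This MMRM applies to height (SAP Section 7.3: "MMRM analysis will also be performed for changes from baseline and changes in Z-Scores from baseline"), to weight in the same terms (Section 7.2), and to BMD and BMC with height-adjusted Z-scores added (Section 7.4). Everything else in those three sections is descriptive, by visit.

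Elsewhere the SAP thinks in terms of one year. Section 2.4 bases the sample size on the precision of annual or 1-year changes; for height at ages 2 to 9 it states "53 completed subjects per treatment group, the 95% CI for the treatment difference will have a precision of 0.11". Section 1 lists the key endpoints of the interim analyses as "change in BMD z-score at Month 12, change in height z-score at Month 12 and change in weight z-score at Month 12".

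**The concern.** Once treatment-by-visit is in the model, the treatment LS-mean difference is an unweighted mean of the visit-specific differences. It equals the Month 12 difference if the effect is the same at every post-baseline visit, and otherwise only by coincidence.

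A constant effect is not the natural expectation here. The primary objective concerns growth and bone mineralization, which change slowly, and Protocol Section 16.1 defends the 1-year duration partly because measurable DEXA change takes time. One fifth of the weight in the height and weight average goes to Month 1 (Day 30), which lies inside titration; footnote a of the Time and Events Schedule reads "Includes a titration period of approximately 6 to 8 weeks, followed by a maintenance period". If the deficit accumulates, the reported difference understates the 1-year deficit. For a safety question that is the unwelcome direction of error.

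**Working it through.** **1. Reproduce the plan's own precision.** Inputs are from SAP Section 2.4. Half-width = 1.96 × SD × √(2/n).

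- Height Z, ages 2 to 9: 1.96 × 0.28 × √(2/53) = 0.107 (stated 0.11).
- Weight Z: 1.96 × 0.43 × √(2/100) = 0.119 (stated 0.12).
- BMD Z: 1.96 × 0.40 × √(2/100) = 0.111 (stated 0.12, which is matched only by rounding up; a side issue).

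The SDs for height and weight are for 1-year changes and the BMD SD is for annual change, so these are precisions for a 1-year difference, not for a visit average.

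**2. Confirm what the LS-means request returns.** The SAP's mean model was fitted to simulated data. The visit-specific differences were -0.022, -0.148, -0.336, -0.439 and -0.567. Their equal-weight mean is -0.302, against -0.567 at Month 12.

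**3. Average as a share of the Month 12 difference.** Visit days are the SAP Section 3.1 targets. For linear build-up:

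- Height and weight: (30 + 90 + 180 + 270 + 360)/5 = 186, and 186/360 = 0.517.
- BMD: (180 + 360)/2 = 270, and 270/360 = 0.75.

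The same calculation for other assumed time courses, applied to the Section 2.4 topiramate-arm changes (-0.18 for height Z, -0.59 for weight Z) as if levetiracetam produced no change:

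| Time course (assumed) | Height/weight share | BMD share | -0.18 (height) becomes | -0.59 (weight) becomes |
|---|---|---|---|---|
| Quadratic | 0.376 | 0.625 | -0.068 | -0.222 |
| Linear | 0.517 | 0.75 | -0.093 | -0.305 |
| Square root | 0.672 | 0.854 | -0.121 | -0.397 |
| Linear to Month 6, then flat | 0.733 | 1.00 | -0.132 | -0.433 |
| Constant | 1.00 | 1.00 | -0.18 | -0.59 |

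(0.733 = (1/6 + 1/2 + 1 + 1 + 1)/5, and 0.59 × 0.733 = 0.433.)

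**4. Width of the averaged interval.** Half-width = Month 12 half-width × √(w′Cw), where w holds equal weights and C is the covariance matrix scaled so that the Month 12 variance is 1. The documents give no C, so a range was used.

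| Assumed covariance | √(w′Cw), 5 visits | Height | Weight | √(w′Cw), 2 visits | BMD |
|---|---|---|---|---|---|
| Proportional to min(s,t) | √0.330 = 0.574 | 0.061 | 0.068 | √0.625 = 0.791 | 0.088 |
| Variance proportional to time, correlation 0.7 | √0.347 = 0.589 | 0.063 | 0.070 | √0.6225 = 0.789 | 0.087 |
| Constant SD, correlation 0.5 | √0.60 = 0.775 | 0.083 | 0.092 | √0.75 = 0.866 | 0.096 |
| Constant SD, correlation 0.9 | √0.92 = 0.959 | 0.102 | 0.114 | √0.95 = 0.975 | 0.108 |

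**5. Does the average lose detection?** For height at 53 per arm, the Month 12 standard error is 0.1066/1.96 = 0.0544, so z = -0.18/0.0544 = -3.3. For the average, z is -0.093/(0.0544 × 0.959) = -1.8 under linear build-up with the widest covariance, and -0.18/(0.0544 × 0.574) = -5.8 under a constant effect with the narrowest. The direction is not fixed.

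**6. Does the averaged interval cover the Month 12 difference?** This was simulated under linear build-up, variance proportional to time and autoregressive-type correlation of 0.5 to 0.9. The averaged interval covered the Month 12 difference in 7% to 28% of trials for height, about 0% for weight, and 79% to 82% for BMD (with an illustrative Month 12 difference of -0.20). The Month 12 contrast covered it in 94% to 96%.

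**The case against.** The strongest reply is that this is an incomplete example rather than a specification. The code is labelled an example, and it saves an ODS table called `estimates` although no ESTIMATE statement is printed, so by-visit contrasts may have been intended. The model line also asks for `solution`; if Month 12 sorts last, the treatment coefficient it prints is the Month 12 difference. The MMRM is called a sensitivity analysis, no formal testing is planned, and the by-visit tables give n, mean and SD per arm, from which a reader could compute an unadjusted Month 12 interval. The Month 12 endpoints in Section 1 describe interim analyses already done. The illustrative sizes rest on assumed time courses and on single-arm changes, and the height illustration uses ages 2 to 9 whereas the model pools all ages.

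Much of this stands as a limit on seriousness. It does not remove the problem. Nothing printed supplies the missing contrast. `solution` prints no confidence interval without CL, and the sort order of visits is not stated. An interval that readers must derive for themselves is not a planned analysis. With no testing and no other between-arm interval in Sections 7.2 to 7.4, the MMRM intervals are the comparative evidence for the primary objective. Ages 2 to 9 is one of the height groups named in Protocol Section 11.4, so that illustration is relevant, though it is not an output of the pooled model.

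**Conclusion.** The concern holds and should be fixed. Run as printed, the code gives an interval for a different quantity from the one the protocol promised and the study was sized on. That mismatch needs no assumption beyond an effect that varies over visits.

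Its size does need assumptions. Across the time courses examined, the average is 38% to 100% of the Month 12 difference for height and weight and 63% to 100% for BMD; linear build-up gives 52% and 75%. The converted values for height and weight also assume no change on levetiracetam. The averaged interval is valid for the average, and a loss of detection cannot be claimed in general.

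**What to change.** Replace the LS-means line with `lsmeans trt*visit / diff cl`, keep the within-visit treatment pairs and save the `diffs` table, or write one ESTIMATE statement per visit with CL. State in SAP Section 7 that treatment differences and 95% intervals are reported at each visit. Name Month 12 as the main contrast, with the other visits alongside; this goes a step beyond the protocol wording but follows from Section 2.4. The all-visit average may stay as a labelled supplementary summary.

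The cost is one or two lines of code, one phrase of text and wider intervals at the planned numbers: height ±0.107 against ±0.061 to 0.102, weight ±0.119 against ±0.068 to 0.114, BMD ±0.111 against ±0.087 to 0.108. Enrollment stopped early, so actual intervals will be wider still; at an assumed 30 per arm the Month 12 height interval is 1.96 × 0.28 × √(2/30) = ±0.142.
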